**Primary Investigator:**

[name]

Professor of Medicine

[name]

Division of Gastroenterology and Hepatology

Department of Medicine

University of North Carolina

[name]

[contact]

Email: [name] [[contact]](mailto:[contact])

**Sponsor:** The University of North Carolina at Chapel Hill

**Grant Number:** 1R21NR017908 - 01A1

**Funded by:** National Institutes of Health –National Institute of Nursing Research (NINR)

**Version Number:** v.7.0

**Version Date:** 16 Nov 2021

**STUDY PROTOCOL  
DOCUMENT HISTORY**

Document	Date of Issue	Summary
Original Version of Protocol, Version 1.0	22Sept2019	
 
• First version of the protocol : 22Sept2019
 
• Submitted to UNC IRB: 22Sept2019
 
• Approved by IRB
 
• Submitted to NINR
 

Version 2.0	07Feb2020	
The following changes have been made:
 
 
• Updated: 
 
○ exclusion criteria
 
○ reimbursement procedures
 
○ randomization procedures
 
○ salivary cortisol procedures
 
○ research team information
 
 
 
• Removed: 
 
○ use of study website; replaced with a Google drive
 
○ use of Zoom; study will only utilize WebEx
 
 
 
• Clarified research staff roles in study procedures
 

Version 3.0	20Mar2020	
**During the COVID-19 outbreak, Wave 1 is allowed to forego saliva sample testing, if necessary, pending allowed research operations**
 
Additionally, the following changes have been made:
 
 
• Recruitment and consenting procedures clarified and updated to include verbal telephone consent
 
• Changed randomization groups so that Group 1 will consist of 7 patients and Group 2 will consist of 9 patients; total number of participants remains the same (n=32)
 
• Updated location of some study procedures to be conducted in a private area and for study documents to be stored in locked, secure area
 
• Minor updates to IT's role and responsibility
 
• Typographical and grammatical errors corrected throughout
 

Version 4.0	18May2020	
The following changes have been made:
 
 
• Removed: 
 
○ use of Google drive; replaced with UNC OneDrive
 
 
 
• Typographical, formatting, and grammatical errors corrected throughout
 

Version 5.0	09Jul2020	Replacing UNC OneDrive with Google Drive due to technical issues.
Version 6.0	15Dec2020	
The following changes have been made:
 
 
• Updated order of study outcomes
 
• Typographical, formatting, and grammatical errors corrected throughout
 

Version 7.0	16Nov2021	Updated study outcomes

## 1 BACKGROUND AND RATIONALE

**Hepatitis C viral (HCV) infection has a tremendous impact on individual and public health.** HCV affects over 3 million Americans, leading to 15,000 deaths per year from liver failure, cirrhosis, and liver cancer. Up to 20% of patients will develop cirrhosis and 10-20% will develop decompensated cirrhosis or cancer. Though typically associated with the liver, HCV is a multi-faceted systemic disease also affecting multiple organs and systems and associated with many extrahepatic disorders (EHDs) including musculoskeletal, endocrine, neuropsychiatric, and cardiac disorders. Our PROP UP data suggest that HCV patients have an average of 4 comorbidities (range: 0-15), the most prevalent being musculoskeletal pain and high blood pressure (50%), psychiatric (44%), sleep disturbance (31%), and diabetes (20%). Patients report clinical distress from somatic and neuropsychiatric symptoms with fatigue, depression, sleep issues and chronic pain most common. Not surprisingly, HRQOL is impaired. While HCV may lead to chronic systemic inflammation with neuropsychiatric and somatic sequelae, other factors also contribute to poor health including social determinants of poor health. Unhealthy lifestyle habits also perpetuate chronic illness and confer greater risk for liver disease, metabolic syndrome, and death. Even in patients cured of HCV, many remain symptomatic and at risk for cirrhosis or liver cancer if healthier lifestyles not adopted. The economic burden of HCV is >\$10 billion annually when accounting for costs of liver disease, EHDs, low HRQOL and loss of work productivity.

**People who have been infected with HCV may benefit from comprehensive multi-modal interventions to improve important patient outcomes.** Comprehensive multi-modal psychosocial interventions that provide stress management, coping skills, and lifestyle modification for the HCV population are nonexistent. Despite chronic health risks, multi-morbidities, life stress and unhealthy behaviors, all of which amplify illness, virtually no psychosocial interventions have been developed for the HCV population. However, evidence-based psychosocial interventions have improved diverse health outcomes in people with other chronic illnesses (e.g., cancers, diabetes, chronic fatigue, pain, HIV). Group-based psychosocial interventions that emphasize cognitive behavioral (CB) stress management (SM) coping skills improve psychological and physical health outcomes and are associated with change in multiple stress-related immunological indices (e.g., CD4 viral count, cortisol patterns, proinflammatory cytokines). Improvements in immune functioning often correlate with symptom reduction. In one of the only psychoneuroimmunological studies conducted in HCV, associations were found between patients' depression, anxiety, fatigue, and pain levels and high levels of inflammatory proteins, accounting for up to 40% of the variance in symptoms.

Extrapolating from this strong empirical base built in other chronic diseases, liver disease researchers need to determine if psychosocial interventions confer similar benefits to liver patients. Given the prevalence of HCV and the number of patients who remain symptomatic or may progress to advanced liver disease, comprehensive, holistic liver care should integrate health promotion interventions into current practice, over and above a myopic focus on just viral eradication and medical management of cirrhosis. The ideal intervention would include stress management, coping skills, and health behavior modifications, which, in turn, may improve symptoms, HRQOL, and disease markers. Within this secondary prevention model, modifying psychological and physiological stress and lifestyle behaviors in symptomatic or at-risk liver patients, may yield substantial health benefits. As such, we sought to tailor evidence-based psychosocial interventions to the needs of HCV patients to improve physical and psychological health outcomes.

**Multiple patient barriers exist to attending *in-person* interventions.** Patient-level barriers to accessing traditional face-to-face healthcare services are enormous and include travel, geographical, financial, transportation, and illness barriers. This dilemma is particularly salient in rural areas where healthcare access is poor. During pilot-testing of the *in-person* group-based Cognitive Behavioral Coping Skills (CBCS-HCV) intervention developed for patients infected with chronic HCV, patients who declined participation cited travel distance and transportation barriers. No patients declined due to lack of interest. Many commented that the intervention seemed valuable, but that *in-person* sessions were impractical. Other psychosocial interventions for patients with HCV that require *in-person* sessions have also suffered from low recruitment, convincing us that alternative modes of delivery

must be explored to increase access to treatment, especially in rural states like North Carolina (85 out of 100 counties are designated rural).

**Delivering interventions via videoconferencing (VC) technology is a cutting-edge alternative to *in-person* delivery.** Healthcare delivery is moving rapidly in the direction of utilizing innovative technologies to overcome myriad inefficiencies costs, and barriers that currently stymy the US healthcare system. “Telehealth” is a burgeoning sector of healthcare delivery in the US. VC technology has numerous potential advantages for delivering interventions directly from providers to patients situated in their own homes. Geographical, financial, and unreliable transportation barriers are eliminated. Patients who are too ill to travel can participate. Reducing patient barriers may lead to higher rates of study enrollment and attendance. Recruitment for *in-person* interventions is often lower than 40%, while recruitment for phone- or web-based interventions can range from 57-94%. Higher attendance may increase intervention “dose,” which in turn, may increase clinical effectiveness. Patient satisfaction with VC has been shown to be very high and often is preferred over *in-person sessions* due to overcoming many obstacles. Importantly, skill-based psychosocial treatments are commonly delivered in a group format, and can be highly economical and efficient for providers and healthcare systems. Delivering psychosocial skill-based interventions in group formats also capitalize on positive therapeutic processes such as group cohesion, peer support, bonding and social persuasion. In order to retain cost-efficiency and beneficial processes of group-based therapy, an ideal telehealth version of the CBCS-HCV would be delivered via VC technology to a group of HCV patients, *participating from the comfort of their own home*. While many telehealth modalities are being investigated, most are 1:1 provider-to-patient; very few have investigated delivering a group-based intervention to multi-end-user patients in their own separate homes.

Since the CBCS-HCV is a skill-based intervention and group format is often the standard of care for these types of interventions, multi-user VC delivery may be a cutting edge and efficient system to deliver holistic interventions to patients who might not otherwise have access to services due to illness or transportation barriers. Pilot testing the CBCS group-based intervention via a state-of-the-art VC multipoint platform is a highly innovative and a logical extension of our previous work. Delivering the CBCS-HCV via VC may decrease patient barriers, increase access to care, and be clinically effective. However, the feasibility, technical issues, patient satisfaction, and preliminary outcomes require pilot-testing to determine if a larger efficacy trial is warranted.

We propose to conduct a pilot feasibility study of a small randomized controlled trial (RCT) to evaluate the CBCS delivered via videoconferencing (herein referred to as “VC-CBCS”) compared to patients in standard of care (SC) with a representative sample of 32 symptomatic HCV patients, to address the following specific aims:

## **2 STUDY AIMS**

**Aim 1:** Evaluate the feasibility of conducting a RCT of the VC-CBCS, quantified as the proportion of patients (a) approached vs. consented vs. enrolled/randomized vs. retained, and (b) who complete data collection;

**Aim 2:** Evaluate the feasibility of intervention delivery via VC, quantified as (a) the proportion of sessions attended by participants and (b) frequency and nature of technical, logistical, or participant problems;

**Aim 3:** Evaluate patient acceptability and satisfaction;

**Aim 4:** Explore changes in patient outcomes, mediators and intervention targets, as well as temporal associations and strength of associations among variables in a preliminary conceptual model, to inform a future efficacy trial.

## **3 STUDY DESIGN**

### **3.1 Study Design**

This pilot feasibility study was designed as a preparatory two-arm small randomized controlled trial (RCT) with a total enrollment of 32 participants assigned by randomization to VC-CBCS (n=24) or SC (n=8) to address the specific aim.

### **3.2 Study Participants**

Participants (n=32) will be a representative sample of adult patients, age 21 or older, who have or had a diagnosis of chronic HCV

### **3.3. Inclusion/Exclusion Criteria**

#### **3.3.1. Inclusion**

- Age 21 and older;
- Medically cleared by hepatology;
- Patients who are currently or were previously diagnosed with chronic HCV;
- Evidence of ongoing symptoms, stress, or unhealthy lifestyle habits, defined as a score of greater than or equal to 4 on a scale 0(none) - 10 (severe) on two or more numeric rating scale questions (see Screening Form 1);
- Able to read and speak English.

#### **3.3.2. Exclusion**

- Decompensated liver disease (Childs Pugh C) judged by hepatologist or recorded in patient medical record;
- Life expectancy of <12 months estimated by hepatologist;
- Has had a liver transplant or is on the waitlist for a transplant;
- Severe alcohol or substance use disorder, psychiatric disorder or cognitive impairment that is likely to interfere with the ability to participate in telehealth groups and follow guidelines about group participation as judged by the Hepatology provider or research staff using a two-tiered research screening process (See Section 6);
- Lack of private, quiet space in home in which to participate in VC-CBCS sessions; and
- Unwilling to have group sessions audio-recorded.

## **4 RECRUITMENT**

A two-pronged recruitment strategy will be utilized (primary: in person in liver clinic; secondary: over the phone). Patients will be recruited from the outpatient liver clinics or by phone if referred by a hepatology provider.

For every patient approached for recruitment, a minimal amount of data will be stored in a REDCap Screening Database, separate from the REDCap Research Database. The Screening Log will include: name, MRN, phone number, race, sex, age, and reason for exclusion or not proceeding forward with consent process. Name, MRN and phone number will be deleted after recruitment ends. De-identified race, sex, and age are retained to satisfy CONSORT guidelines for future publications.

Patients will be recruited in 4 waves. Although we seek to enroll/randomize a total of 32 patients with 24 randomized to VC-CBCS and 8 randomized to SC, we will over-consent to accommodate for patients who are deemed ineligible during the screening process or who withdraw consent prior to enrollment. The overall 3:1 randomization scheme allows us to examine feasibility of randomization while allowing us to intensively examine the VC-CBCS group.

## 5 INFORMED CONSENT PROCESS

The informed consent process will take place in person in the GI liver clinic or over the phone.

1. **In-Person Consent:** Interested patients will be introduced to study staff and taken to another private room to engage in the informed consent process and screening assessment. Interested and eligible patients will sign and date/time the consent forms, staff signs/dates and the patient will be provided a copy. The informed consent process will be documented for each consented patient. After written consent is obtained, staff can begin to screen and collect data from the patient.
2. **Over-the-Phone Consent:** When a prospective patient is referred by a hepatology provider to the study team, the staff will pre-screen the patient using a limited waiver of HIPAA approved by the UNC IRB. Study staff will access patient medical records for contact information and conduct a brief eligibility assessment (e.g., HCV diagnosis, > age 21, English speaker). Staff will contact patients via phone to discuss the study and consent documents. Interested patients will be consented with a verbal telephone consent and then be emailed or mailed a HIPAA authorization with a pre-paid envelope for return. The study team will then review the HIPAA authorization with the participant and instruct the participant to sign and date and return to study in provided envelope. Participants will be considered consented if and when they agree to the telephone verbal consent, but their medical records will not be accessed until signed HIPAA authorization is received by the study team.

Whether consented in-person or over the phone, all components of the informed consent process will be reviewed and documented per federal (<https://www.hhs.gov/ohrp/regulations-and-policy/regulations/finalized-revisions-common-rule/index.html>) and institutional guidelines (<https://www.hhs.gov/ohrp/regulations-and-policy/regulations/finalized-revisions-common-rule/index.html>) and relevant Good Clinical Practice Guidelines from the International Conference on Harmonisation. Issues of privacy, confidentiality, and time commitment will be discussed. Patients will verbalize understanding that research participation is voluntary and they can choose to stop or decline at any time without penalty. They can refuse to participate, and this decision will not affect their medical care at UNC. They can refuse to answer any study or interview question. The study staff obtaining consent will allow ample time for patients to ask questions and express full understanding of the study.

A checklist of the informed consent process will be retained for all consented patients. All signed consent forms will be uploaded to the REDCap database and hard copies retained in a secure location. Data collection, enrollment, randomization will not commence until all necessary consents have been obtained.

Patients will consent to participate in the following:

- 1) review of electronic medical records for clinical data;
- 2) undergo screening process and collection of screening data;
- 3) participation in a 14-week VC-CBCS group intervention delivered via home technology or study-loaned tablets that patients may return at the end of the study;
- 4) participation in a group exit interview following participation in the intervention;
- 5) completion of self-report surveys throughout the study;
- 6) collection of saliva samples at pre- and post-intervention; and
- 7) REDCap storage of email address, mailing address, phone numbers for self and a loved one in case of lost to follow-up. This information is required for REDCap data collection of surveys, reimbursement to patients and communication throughout the study.

## 6 SCREENING FOR VC-CBCS ELIGIBILITY

To enhance intervention fidelity, group cohesion/dynamics, and adherence to the protocol, a two-tiered screening process will be conducted to enroll eligible patients. Patients will be consented prior to engaging in the screening assessment. Phase I of screening will occur with study staff in-person in the liver clinic or over the phone. Phase II is conducted by the study PI.

**6.1 Phase I Screen:** Staff will conduct the initial screening for I/E criteria using three Screening Forms located in a separate REDCap database for screening data only. The patient must meet all inclusion criteria including "evidence of ongoing symptoms, stress, or unhealthy lifestyle habits as defined by a score of  $\geq 4$  on a rating scale from 0 – 10, for  $\geq 2$  symptoms, perceived stress, or lifestyle habits" and must not meet exclusion criteria, including severe current alcohol, substance use or psychiatric disorder likely to interfere with group dynamics or adherence to study protocol. The Screening Forms will include items to determine inclusion/exclusion criteria, including assessment of physical and mental symptoms, stress level, and lifestyle habits. Alcohol, substance use, and psychopathology will be assessed using questions from validated instruments, including the Alcohol Use Disorders Identification Test (AUDIT), the Substance Abuse and Mental Illness Brief Symptom Screener (SAMISS) and additional screening items developed by the PI. Screening will take place in-person in private exam room in clinic, or over the phone.

**6.2 Phase II Screen:** The second phase of the two-tiered screening process will be conducted by the PI (a licensed clinical psychologist at UNC Healthcare) who will review the Phase I screening forms and discuss the prospective participant with the screening coordinator who conducted the consent and screen. If the patient meets I/E criteria and screens negative for severe current alcohol, substance use or psychiatric disorders, the patient will be approved for enrollment into the study based on Phase I screening data. When ambiguity or uncertainty arises regarding the patient's eligibility related to current alcohol, substance use or psychiatric disorders, the PI will conduct a brief clinical interview with a prospective participant over the phone. Based on the two-tiered screening process, the PI will adjudicate final decisions regarding study eligibility.

The goal of the two-tiered screening process is to ensure that patients (1) are appropriate for a group therapeutic setting; (2) are at low risk for verbal behaviors that will interfere with or sabotage group cohesiveness/support which is critical to the success of psychosocial interventions; (3) are able to adhere to the study protocol and rules of engagement; and (4) with active and severe psychiatric or substance use disorders are referred for more appropriate individual treatment in their local community.

Patients judged to have untreated or more severe psychopathology will receive a referral from the PI to more appropriate mental health/addiction services in their local community.

**6.3 Screening Data:** Data from the three Phase I Screening Forms will be stored in a REDCap screening database separate from the Research Data. For patients who are ineligible or decline to participate, their name, MRN, age, sex, race, and reason for ineligibility/refusal will be retained in the screening REDCap database. All other screening data will be deleted at the end of the study. Name and MRN are retained during the study for staff to identify previously recruited but ineligible patients. Name and MRN of non-enrolled patients will be deleted from the screening database after recruitment ends. The hard copy Phase II Brief Clinical Interview forms will be shredded after recruitment ends. Once the screening data are deleted or de-identified, only sex, race, age, and reason for non-enrollment patients will be retained until all data are published, to satisfy CONSORT guidelines. Once final data are published, the REDCap Screening database will be deleted. For patients who are eligible and enrolled, data from the three Screening Forms will be exported into the Research REDCap database to describe characteristics of the cohorts.

## 7 REIMBURSEMENT

Participants in both conditions will be reimbursed \$25 for four patient-reported outcomes (PROs) assessments and two days of salivary sample collection. Completion of PROs during each assessment period will take 20-30 minutes. Patients randomized to VC-CBCS will be reimbursed \$25 to participate in an exit focus group. For reimbursement of VC-CBCS sessions, participants will be reimbursed for cellular and wi-fi data plans, if needed for iPad use, and will be given two options: (1) retain the iPad (worth \$300) after the study ends; (2) receive a rechargeable Visa gift card at the beginning of the study that will be recharged with \$300 after the intervention ends and iPad is returned. Participants will check their preference for one of these two options on the consent form. Participant preferences will be tracked in a Reimbursement Log to inform reimbursement options for a future RCT.

## 8 RANDOMIZATION

Four groups of patients will be randomized and will consist of 7-9 patients each. The groups are as follows:

- Group 1 - 7 patients with 5 randomized to VC-CBCS and 2 to SC;
- Group 2 - 9 patients with 7 randomized to VC-CBCS and 2 to SC;
- Groups 3 and 4 - 8 patients each with 6 randomized to VC-CBCS and 2 to SC each group.

Once each group meets their respective necessary number of patients, they will be randomized. We will use these randomization procedures for a total of 24 participants randomized to VC-CBCS and 8 randomized to SC and overall 3:1 ratio. A computer-based procedure for permuted-block randomization and concealment will be implemented by non-study staff. No study personnel will have access to the randomization schedule. The computer-generalized randomization scheme will automatically randomize patients who are enrolled to one of the two group assignments after each wave is enrolled. Participants will be subsequently called and informed of group assignment.

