**Figure 1: Conceptual Model of VC-CBCS Intervention**

## 10.2 Conducting the VC-CBCS Group Intervention

Sessions will be delivered using the UNC School of Medicine's University-approved, HIPAA-compliant WebEx® videoconferencing system. WebEx® is an application that is widely used for web and videoconferencing meetings and includes multi-point audio and video communication, screen sharing, video and audio recording, and telephone bridging. The research team will work closely with the UNC School of Medicine Information Technology Security Team on all aspects of delivering the VC-CBCS including patient instructions, iPad set up, and remote data cleaning. Each group member will join the virtual group from their home using their choice of home audio-visual technology or study-provided iPads to simultaneously observe and interact with the group facilitator and other group members ("Brady Bunch" style).

All modules follow the same three-part organization (**Table 1**):

- (1) Introduction and practice of new relaxation skill
- (2) Review of previous weeks' information, skill, and SMART goals
- (3) Information, acquisition, and practice of new skills. Didactic information is followed by practicing skills to aid in cognitive behavior change. Motivational enhancement strategies are used to increase personal and social motivation. SMART goals are used to promote achievement of weekly goals that are specific, measurable, action-oriented, realistic, and time-based.

VC-CBCS sessions will be led by a Masters-level therapist with experience in facilitating groups, protocol-based and evidence-based treatments, and adept at motivational enhancement strategies.

[figure not shown]
VC-CBCS patient materials will be stored on iPads and uploaded to a secure Google Drive shared drive containing no identifying information. Materials include the Patient Workbooks, relaxation audio-recordings, technical instructions, and link to unique REDCap application system. Hard copy *Patient Workbooks* will also be mailed to each participant prior to the first session for use during sessions.

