### **10.4 Iterative changes to VC-CBCS intervention**

Based on patient feedback and lessons learned, the research team will modify aspects of the VC-CBCS in-between the four waves. Changes may be made based on feasibility data, patient satisfaction ratings, and impromptu feedback, feedback from exit focus groups and overall experiences and lessons learned. Consideration for making *substantial* changes during the trial would occur if major issues were identified that seriously jeopardize recruitment, attendance, retention, or data collection efforts. Otherwise, we will carefully track issues during each wave, making minor changes to improve performance, and solicit feedback about issues during exit focus groups. If recruitment, attendance, and retention are not hugely jeopardized, the team may wait to make substantive changes until after all the feasibility, patient acceptability, and exit focus group data are analyzed.

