**12.2 Patient Satisfaction (Aim #3)**

To address specific aim #3, several measures of patient satisfaction will be collected. VC-CBCS patients will complete a Patient Acceptability/Satisfaction survey after each of the 14 sessions. They will complete a survey on satisfaction with therapist and group dynamics midway through and at end of the intervention. Reasons for drop out and attrition will be evaluated in both conditions. Exit group interviews will be conducted with each VC-CBCS cohort after the intervention ends and will be audio-recorded. The audio recording will be stored on a secure network server housed by UNC. The qualitative data will be analyzed to understand likes/dislikes, pros/cons, and solicit feedback on optimizing the intervention (e.g., number and duration of sessions, modules, relaxation skills, structure, group format, data collection). For the Patient Acceptability/Satisfaction Survey, items are scored on a scale from 1= not at all to 5=extremely. Data across all patients and all sessions will be averaged into a Total Patient Satisfaction

score that could range from 1 to 5 with higher scores indicating greater satisfaction. *One secondary outcome is the overall Patient Acceptability/Satisfaction survey mean score from all patients over all 14 sessions.*

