### **23.4 Aim 3: Patient satisfaction and acceptability**

Qualitative data from each exit focus groups will be obtained to help improve the structure and content of the future VC-CBCS and study methods. The Patient Acceptability/Satisfaction survey will be analyzed as an average for the 14 sessions. Items on the group dynamics survey will be evaluated at both time points. Reasons for drop out will be evaluated in both conditions. *We anticipate that patients will find the VC-CBCS highly acceptable and useful, as measured by the Patient Acceptability survey and information provided during the exit focus groups.* If 19 of the 24 VC-CBCS participants find the intervention acceptable (overall score  $\geq 3.5$  out of 5.0), the point and interval estimate will be 79% [95% CI: 61, 100].

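### VC-CBCS patients appear to be treated in four groups of 5 to 7, but section 23 treats them as 24 independent people; this affects intervals for VC-CBCS means modestly and exact binomial intervals little

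*Combined protocol and SAP*

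**What the plan says.** Section 4 states "Patients will be recruited in 4 waves". Section 8 adds "Once each group meets their respective necessary number of patients, they will be randomized" and fixes the split for each wave, starting with "Group 1 - 7 patients with 5 randomized to VC-CBCS and 2 to SC". Wave 2 is 7 and 2, and waves 3 and 4 are 6 and 2 each, giving 24 VC-CBCS and 8 SC.

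In section 10.2, VC-CBCS patients join a virtual group in which they "simultaneously observe and interact with the group facilitator and other group members". Section 12.2 says "Exit group interviews will be conducted with each VC-CBCS cohort after the intervention ends". Under section 10.4, "the research team will modify aspects of the VC-CBCS in-between the four waves". Section 1 argues that group formats "capitalize on positive therapeutic processes such as group cohesion, peer support, bonding and social persuasion".

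Section 23.1 plans no hypothesis tests and reports estimates with 95% confidence intervals or standard deviations. Sections 23.2 to 23.5 mention no wave factor, therapy-group term or ICC. The serial correlations in 23.5 concern repeated measures on one person. The only worked interval, in 23.4, supposes that 19 of 24 VC-CBCS participants find the intervention acceptable: "the point and interval estimate will be 79% [95% CI: 61, 100"].

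**The concern.** People who attend the same 14 sessions with the same peers may come to resemble one another in attendance, retention, satisfaction and symptoms. If they do, 24 patients in four groups carry less information than 24 separate patients, and an interval that ignores this is too narrow. The protocol's own account of how the group works makes such resemblance plausible, but does not establish it.

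A second issue needs no ICC. If the intervention is modified between waves, a figure pooled over waves cannot show whether results shifted after the change.

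The stakes lie in planning. Section 12.3 says the patient-reported data will feed sample size calculations for the efficacy trial, and pooled standard deviations give no sign that a group design effect must be added.

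The point covers VC-CBCS-only results formed after grouping: retention (13.4), session attendance (23.3), acceptability and satisfaction (15.7, 23.4), and VC-CBCS T4 and change scores. It does not touch consent and randomisation percentages (13.1, 13.2), baseline values or SC-only results.

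**Working it through.** **Inputs.** VC-CBCS group sizes 5, 7, 6, 6 (section 8); 19 of 24 and the limits 61 and 100 (section 23.4); anticipated retention above 80% (section 23.2). ICCs of 0.01, 0.05 and 0.10 are assumptions.

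**1. The plan's own figure.** 19/24 = 79.2%. The exact (Clopper-Pearson) one-sided 95% lower limit is the p that solves P(X ≥ 19 | n = 24, p) = 0.05, which is 61.1%. With the upper limit set to 100%, this reproduces the stated interval. It is thus a one-sided bound for independent people. The two-sided exact interval is 57.8% to 92.9%.

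**2. Design effect.** The size-weighted group size is (25 + 49 + 36 + 36)/24 = 146/24 = 6.08, so DEFF = 1 + 5.08 × ICC. Intervals for a mean widen by √DEFF.

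| Assumed ICC | DEFF | √DEFF | Naive 95% coverage, VC-CBCS mean |
|---|---|---|---|
| 0.01 | 1.05 | 1.025 | 94.4% |
| 0.05 | 1.25 | 1.120 | 92.0% |
| 0.10 | 1.51 | 1.228 | 89.1% |

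Coverage comes from simulation of normal data in these four groups (60,000 runs). Multiplying the interval by √DEFF at the true ICC restores it to about 95%. If 80% are retained, the size-weighted group size is about 5.0, DEFF is 1.04, 1.20 and 1.40, and intervals widen by about 2%, 10% and 18%.

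**3. Exact binomial interval.** With a beta-binomial model for each group and a true proportion of 19/24, the exact one-sided 95% bound covers 97.3% under independence, and 97.0%, 95.8% and 94.1% at the three ICCs. The two-sided exact interval covers 98.0%, then 97.6%, 96.2% and 94.4%. Protection is not uniform: at ICC 0.05 the one-sided coverage falls to about 93% at some true proportions between 0.60 and 0.95, although its average over that range is 96.4%.

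**4. Pooled standard deviation.** E[s²]/σ² = (24 − DEFF)/23 = 0.998, 0.989 and 0.978. Taking square roots, the SD is understated by 0.1%, 0.6% and 1.1%.

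**5. Can the trial estimate the ICC?** With a true ICC of 0.05, the analysis-of-variance estimate from four such groups ranges from −0.18 to 0.41 (2.5th to 97.5th percentile) and is zero or negative in 47% of simulations. It cannot.

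**The case against.** The strongest reply is that little turns on this. No tests are planned, 19/24 is a hypothetical example, and every magnitude rests on an ICC that the documents do not supply and the trial cannot estimate. At ICC 0.01 the effect is negligible. All of this stands, and it sets the severity.

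Intervals for retention and attendance are not specifically planned either: 23.2 tabulates frequencies, 23.3 summarises descriptively, and 23.1 allows either intervals or standard deviations. That stands too, so for these outcomes the remedy is only a by-wave table.

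Section 10.4 already has the team track issues in each wave, and holds substantial changes during the trial to serious problems. This is partly an answer. But it is operational tracking, and section 23 plans no results by wave.

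A reader might infer that the 61% limit is too optimistic and should be recomputed on a reduced sample size. The coverage in step 3 does not support that: at 19/24 the exact bound still exceeds nominal coverage at ICC 0.05 and is about one point short at 0.10, and the reduced-sample version over-covers (about 98% to 99% on average).

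A reader might also infer that the between-arm comparison needs wave as a factor. The calculations do not support that. If extra variation is confined to VC-CBCS and makes up 5% or 10% of variance, coverage without wave is 94.2% or 92.9%; adding wave lowers it to 93.7% or 92.0% (baseline correlation of 0.6 assumed). With two SC patients per wave, 80% retention and independent dropout, the chance that some wave loses both is 1 − (1 − 0.2²)⁴ = 15%.

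**Conclusion.** The point holds in a limited form. Section 23 makes no allowance for wave or therapy group in VC-CBCS-only results, although the design creates four groups of 5 to 7 and permits the intervention to change between them. For VC-CBCS means, an ordinary 95% interval would cover about 94%, 92% or 89% at assumed ICCs of 0.01, 0.05 or 0.10. For exact binomial intervals the loss is small and mostly absorbed. Pooled SDs are understated by about 1% or less.

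This rests on the assumed ICC range and on one therapy group per wave, which sections 8, 10.2, 10.4 and 12.2 together imply but do not state outright. The documents do not show that group members are in fact correlated, so it would be wrong to say that the planned intervals are known to be invalid.

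Severity is at the low end of minor: the pilot is descriptive, tests nothing and ties no decision threshold to the interval.

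**What to change.** 1. Report VC-CBCS retention, attendance, acceptability and satisfaction, and T4 means by wave, as descriptive counts and means without by-wave intervals. Mark any change to the intervention between waves.
2. For VC-CBCS-only continuous means (satisfaction score, T4 and change scores), give the 95% interval under independence and also multiplied by √DEFF over a stated ICC range such as 0.01 to 0.10, using the group sizes actually analysed.
3. Label the 19/24 interval as a one-sided exact bound that assumes independence, and give the two-sided exact interval (58% to 93%) beside it. Do not inflate it.
4. State that four groups cannot estimate an ICC reliably, that the pooled SDs are usable for planning, and that the efficacy trial's sample size must apply a therapy-group design effect separately.

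Leave the between-arm estimate as planned.

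The cost is SAP wording and one table from data already held. The second set of intervals for VC-CBCS means is about 2.5% wider at ICC 0.01, 12% at 0.05 and 23% at 0.10 with all 24 analysed. By-wave cells hold only 5 to 7 people (5/6 has an exact 95% interval of 36% to 100%), so the table must be labelled descriptive and not read as a comparison of waves.
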